4.12 Other Data Summaries

Intended method of closure

The intended method of ulcer closure recorded at Study Visit 1 will be cross-tabulated against the actual method of closure recorded for those ulcers that achieve closure, with the remaining ulcers coded as not-closed.

This summary will be repeated including only those wounds that achieved confirmed closure; the remaining ulcer will be coded as not-confirmed closure.

Ulcer Debridement

Whether the target ulcer was debrided, and the type of debridement used, will be summarized by Study Visit and overall. Separately, whether the target ulcer was debrided, and the type of debridement used, will be summarized at Run-In Visit 2.

Interruption of study therapy

Whether the study therapy was interrupted between study visits, and if so, how long for (in hours), will be summarized overall Study Visits by treatment.

Additionally, the total time per subject for which the study therapy was interrupted between study visits will be summarized by treatment.

Interruption of compression therapy

Whether the compression therapy was interrupted between study visits, and if so, how long for (in hours), will be summarized overall Study Visits by treatment.

Additionally, the total time per subject for which the compression therapy was interrupted between study visits will be summarized by treatment.

Resource Use

The dressing applied, kit size used, whether a filler was used, the filler used, will be summarised at each Study Visit and overall. Whether the subject is using any compression therapy or pressure relieving/offloading therapy, and the type of therapy/equipment used will be summarized.

The device therapy mode and pressure setting (continuous), high/low therapy set points and time on/off cycle times (intermittent), and adjustable compression rate will be summarized for ActiV.A.C.® subjects only.

The personnel time taken (in minutes) to apply the NPWT system will be summarized overall Study Visits by treatment, and separated by intermittent/continuous, and by whether any filler dressing was used.

In addition, the total personnel time taken (in minutes) to apply the NPWT system for each subject will be summarized by treatment. A two sample t-test will be used to test for a difference in the mean total time taken (in minutes) to apply the NPWT system between treatments. 95% confidence intervals will also be presented. If the assumptions of the t-test are violated, the Wilcoxon rank sum test will be used instead with Hodges-Lehmann estimates of the median difference and 95% confidence interval reported.

The number of personnel (and type of personnel) applying the device will be summarized overall Study Visits by treatment, and separated by intermittent/continuous, and by whether any filler dressing was used.

Continuing Dressing Usage

Whether any dressings were applied at Study Visit 14 will be summarized by treatment and by whether the ulcer is open / closed at Study Visit 14.

4.13 Safety

All safety analyses and summaries will be conducted using the Safety Population.

Extent of Exposure

The duration of treatment with NPWT will be summarized by treatment.

Adverse Events

Adverse events will be coded and grouped by system organ class using the Dictionary for Medical Drug Regulatory Activities (MedDRA). Adverse event summaries will separately be presented for the screening period, treatment period

Document Number: 1004313

Document Part: 000

Document Version: 06

Document Status: Released

ST:

9 7 5

Reference:

CE/052/PIC

Customer Code:

0 5

(Study Visit 1 – Visit 14) and overall. Unless otherwise stated, all safety summaries will be presented by treatment and wound type (DFU or VLU) and overall.

The number of subjects reporting: adverse events, serious adverse events, severe adverse events, investigational device related adverse events, a serious investigational device related adverse event, an unexpected adverse event and a serious unexpected adverse event. In addition, for each adverse event, the following will be summarized: severity, treatment, NPWT usage, the relationship to the investigational device, the possible cause if related, outcome and duration of the resolved adverse events and the duration of the adverse events at trial discontinuation.

The proportion of subjects with a device-related adverse event will be compared between treatments using Fisher's exact test. In addition, the percentage of serious device related adverse events and the corresponding 1-sided upper 95% confidence limit will be detailed assuming a Poisson distribution for serious device related adverse events separately for each treatment.

The number and proportion of subjects reporting treatment-emergent adverse events split by treatment separately by system organ class, and preferred term will be summarized by:

1. Their relationship with the investigational device (not related or related). If the relationship is missing, the adverse event will be assumed to be treatment-related and a footnote will be added to the table. If a subject experiences more than one preferred term within a system organ class, then the relationship at the system organ class level for that subject will be reported according to their most related relationship for each preferred term.
2. The severity of the adverse event (mild, moderate or severe).
3. Whether or not the adverse event is serious
4. The adverse event outcome.
5. Whether or not the adverse event is expected or unexpected.

Document Number: 1004313
Document Version: 06

Document Part: 000
Document Status: Released

ST:

9 7 5

Reference:

CE/052/PIC

Customer Code:

0 5

Clinical Laboratory Evaluations

The subject blood biochemistry and hematological values, including the numbers of subjects that are below (abnormal), within and above (abnormal) the normal ranges, upon entry to the screening period will be summarized.

Hematology: Red Blood Cell (RBC) count, Hemoglobin, Hematocrit, Platelets, White Blood Cell (WBC) total count, and differential (%) including absolute counts (x 10⁹/L)

Blood Biochemistries: Sodium, Potassium, Calcium, Creatinine, Total Bilirubin, ALT, AST, Alkaline Phosphatase, Albumin, Total Protein, Urea, Glucose, and HbA1c

Additional Chemistries: Pre-albumin

Vital Signs, Physical Findings

The vital signs recorded upon entry to the screening period (including Resting Heart Rate, Respiratory Rate, Blood pressure (systolic and diastolic) and Blood pressure measurement location will be summarized.

Concomitant Medications

The number and percent of subjects that take pre-randomization concomitant medications relevant to the target ulcer will be summarized. The number and percent of subjects who take post-randomization concomitant medications relevant to the target ulcer will be summarized separately for new and existing concomitant medications.

5 References

Lan, KKG and DeMets, DL 1983. *Discrete sequential boundaries for clinical trials*. Biometrika; 70: 659-663.

Mark D. Rothmann, 2011. *Design and Analysis of Non-Inferiority Trials (Chapman & Hall/CRC Biostatistics Series)*. 1 Edition. Chapman and Hall/CRC.

Document Number: 1004313

Document Version: 06

Document Part: 000

Document Status: Released

6 How to Score EQ-5D-5L

The EQ-5D-5L descriptive system should be scored, for example, as follows:

Levels of perceived problems are coded as follows:			
Under each heading, please tick the EQ-5D box that best describes your problem (10000)			
MOBILITY			
I have no problems in walking about			
I have slight problems in walking about			
I have moderate problems in walking about			
I have severe problems in walking about			
I am unable to walk about			
SELF CARE			
I have no problems washing or dressing myself			
I have slight problems washing or dressing myself			
I have moderate problems washing or dressing myself			
I have severe problems washing or dressing myself			
I am unable to wash or dress myself			
USUAL ACTIVITIES (e.g. work, study, housework, family or leisure activities)			
I have no problems doing my usual activities			
I have slight problems doing my usual activities			
I have moderate problems doing my usual activities			
I have severe problems doing my usual activities			
I am unable to do my usual activities			
PAIN / DISCOMFORT			
I have no pain or discomfort			
I have slight pain or discomfort			
I have moderate pain or discomfort			
I have severe pain or discomfort			
I have extreme pain or discomfort			
ANXIETY / DEPRESSION			
I am not anxious or depressed			
I am slightly anxious or depressed			
I am moderately anxious or depressed			
I am severely anxious or depressed			
I am extremely anxious or depressed			
Level 1 is coded as a '1'			
Level 2 is coded as a '2'			
Level 3 is coded as a '3'			
Level 4 is coded as a '4'			
Level 5 is coded as a '5'			

This example operates the health state '13345'

NB: There should be only ONE response for each dimension

NB: Missing values can be coded as '0'

NB: Ambiguous values (e.g. '3' boxes are ticked for a single dimension) should be treated as missing

10000

EuroQol Research Foundation. 2015. EuroQol - How to use EQ-5D. [ONLINE] Available at: <http://www.euroqol.org/about-eq-5d/how-to-use-eq-5d.html>. [Accessed 27 March 15].

7 How to Score Wound Assessment scoring tool (BWAT-M)

Item	Assessment
1. Undermining	1 = None present 2 = Undermining < 2 cm in any area 3 = Undermining 2-4 cm involving < 50% wound margins 4 = Undermining 2-4 cm involving > 50% wound margins 5 = Undermining > 4 cm or Tunneling in any area
2. Necrotic Tissue Type	1 = None visible 2 = White/grey non-viable tissue &/or non-adherent yellow slough 3 = Loosely adherent yellow slough 4 = Adherent, soft, black eschar 5 = Firmly adherent, hard, black eschar
3. Necrotic Tissue Amount	1 = None visible 2 = < 25% of wound bed covered 3 = 25% to 50% of wound covered 4 = > 50% and < 75% of wound covered 5 = 75% to 100% of wound covered
4. Exudate Type	1 = None 2 = Bloody 3 = Serosanguinous: thin, watery, pale red/pink 4 = Serous: thin, watery, clear 5 = Purulent: thin or thick, opaque, tan/yellow, with or without odor
5. Exudate Amount	1 = None, dry wound 2 = Scant, wound moist but no observable exudate 3 = Small 4 = Moderate 5 = Large
6. Skin Color Surrounding Wound	1 = Pink or normal for ethnic group 2 = Bright red &/or blanches to touch 3 = White or grey pallor or hypopigmented 4 = Dark red or purple &/or non-blanchable 5 = Black or hyperpigmented
7. Granulation Tissue	1 = Skin intact or partial thickness wound 2 = Bright, beefy red; 75% to 100% of wound filled &/or tissue overgrowth 3 = Bright, beefy red; < 75% & > 25% of wound filled 4 = Pink, &/or dull, dusky red &/or fills < 25% of wound 5 = No granulation tissue present
8. Epithelialization	1 = 100% wound covered, surface intact 2 = 75% to < 100% wound covered &/or epithelial tissue extends to > 0.5 cm into wound bed 3 = 50% to < 75% wound covered &/or epithelial tissue extends to < 0.5 cm into wound bed 4 = 25% to < 50% wound covered 5 = < 25% wound covered

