9.1 VISITS AND EXAMINATIONS

9.1.1 Screening Run-in Visit 1

Assign a subject ID number to each subject who enters screening.

NOTE 1: Subjects who enter screening should have the potential heal, with excessive edema and infection under control.

NOTE 2: Any subject who signs an informed consent, but fails to meet the required entry criteria is considered to be a Screen Failure. Screen Failure subjects should have their demographic information captured with the reason for screen failure specified. Subjects may be re-screened 2 times. If a subject fails to meet all criteria after 3 screening attempts, the subject may not be enrolled into the study. A new informed consent is required for each screening attempt. All procedures, excluding the central lab, ABI, Toe Pressure, or TcPO₂ obtained within 30 days of re-screening, must be repeated for each screening attempt.

1. Explain the purpose and nature of the study, and have the subject or the subject's legally authorized representative **read, sign, and date** the IRB-approved informed consent document. Additionally, have the individual who obtains consent from the subject sign and date the informed consent document. Provide a photocopy of the signed informed consent document to the subject and place the original signed document in the subject's chart. Documentation of the informed consent process should be captured in each subject's source for each consenting.

----- Do not proceed until consent has been obtained -----

2. Screen the subject against the protocol inclusion and exclusion criteria for eligibility.
3. Obtain basic demographic information and relevant medical history, including information on all concomitant medications.
4. Complete a physical examination, body weight, height, and vital signs, including measurement of resting heart rate, respiratory rate, and blood pressure while seated.
5. Obtain complete history pertinent to the lower extremity target ulcer, including duration of the target ulcer, previous and current treatment and any other history that may have impacted the target ulcer (has it healed and re-occurred in the same location).
6. Assess target ulcer level of pain using the VAS.
7. Perform ulcer debridement if indicated. Debridement may only be performed using a curette, scissors, scalpel, or forceps.

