All responses to the exit survey will be summarized by treatment and by individual tNPWT device. In addition, where appropriate, a Cochran-Mantel-Haenszel test will be used to test for a difference in subject response between treatments for individual survey questions.

Remaining exploratory endpoints, including the estimation of tissue types present, condition of peri-wound skin and the pain on removal of dressing and at initiation of, and during, therapy, will be summarized by assessment and treatment.

CONFIDENTIAL DOCUMENT
This document contains confidential information, which is the property of Smith & Nephew, Inc. Do not copy, disclose, or circulate without written authorization from the appropriate Smith & Nephew personnel

Other Planned Analysis

At minimum, all data collected will be summarized and listed by treatment; where appropriate data collected will also be summarized by tNPWT device. Additional subsets for summaries may be utilized as a result of the analyses relating to the primary and secondary objectives.

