10.4 SAFETY

All safety analyses and summaries will be conducted using the Safety Population. Unless otherwise stated, all safety summaries will be presented by treatment and wound type (DFU or VLU) and overall. All safety analyses will also be separated by tNPWT device.

Extent of Exposure

The duration of treatment with NPWT will be summarized.

Adverse Events

Adverse events will be coded and grouped by system organ class using the Dictionary for Medical Drug Regulatory Activities (MedDRA).

The number of subjects reporting: adverse events, serious adverse events, severe adverse events, investigational device related adverse events, a serious investigational device related adverse event, an unexpected adverse event and a serious unexpected adverse event. In addition, for each adverse event, the following will be summarized: severity, treatment, NPWT usage, the relationship to the investigational device, the possible cause if related, outcome and duration of the resolved adverse events and the duration of the adverse events at trial discontinuation.

The proportion of subjects with a device-related adverse event will be compared between treatments using Fisher's exact test. In addition, the percentage of serious device related adverse events and the corresponding 1-sided upper 95% confidence limit will be detailed assuming a Poisson distribution for serious device related adverse events separately for each treatment.

The number and proportion of subjects reporting treatment-emergent adverse events split by treatment separately by system organ class, and preferred term will be summarized by:

CONFIDENTIAL DOCUMENT
This document contains confidential information, which is the property of Smith & Nephew, Inc. Do not copy, disclose, or circulate without written authorization from the appropriate Smith & Nephew personnel

1. Their relationship with the investigational device (not related or related). If the relationship is missing, the adverse event will be assumed to be treatment-related and a footnote will be added to the table. If a subject experiences more than one preferred term within a system organ class, then the relationship at the system organ class level for that subject will be reported according to their most related relationship for each preferred term.
2. The severity of the adverse event (mild, moderate or severe).
3. Whether or not the adverse event is serious
4. The adverse event outcome.

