4.3 Derived Data

1. A flag for patient inclusion in the full analysis set. If the patient has received NPWT and has at least one (post-baseline) dressing change assessment then the patient is included in the full analysis set. Otherwise the patient is excluded from the full analysis set.
2. A flag for patient inclusion in the safety population. If the patient has received NPWT, then the patient is included in the safety population. Otherwise the patient is excluded from the safety population.
3. The duration in days between the baseline assessment (Randomization Study Visit 1) and each scheduled Study Visit (2-12) (scheduled every 7 days) and Study Visit 13 or 14.

ST:

9 7 5

Reference:

CE/052/PIC

Customer Code:

0 5

4. The duration in days between the Screening Run-In Visit 1 and Screening Run-In Visit 2.
5. A flag for whether the Screening Run-In Visit 2 occurred 7 (± 1) days after Screening Run-In Visit 1.
6. The duration in days between the baseline assessment (Randomization Study Visit 1) and each scheduled Study Visit (2-12) (scheduled every 7 days) and Study Visit 13/14.
7. A flag for whether study visits occurred weekly after the Randomization Visit as per the protocol. A separate flag should be derived for each study visit.
E.g. Study Visit 2 should occur at 7 (± 1) days after the Randomization Study Visit 1. Study Visit 3 should occur at 14 (± 1) days etc.
8. The duration in days between the Study Visits i and j (where $i \geq 1$ and $j = i + 1$)
9. Patient age (years) defined as: The date of the baseline assessment – date of birth/365.25
10. Patient body mass index defined as: $\text{Weight (kg)} / (\text{Height (cm}/100))^2$
11. Reference wound duration at point of randomisation will be derived as follows:
Date of Target onset date - Date of Randomization Visit 1
12. The (post-screening) study duration (in days) will be derived as follows:
Date of Study Completion - Date of Randomization Visit 1
13. The Screening duration (in days) will be derived as follows (separately for screening, re-screen 1 and re-screen 2 where appropriate):
Date of Run-In Visit 2 - Date of Run-In Visit 1
14. The number of screening periods per subject will be derived as:
No re-screening periods used = 1
A single re-screening period used = 2
Two re-screening periods used = 3

Document Number: 1004313
Document Version: 06

Document Part: 000
Document Status: Released

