4.4 Patient Analysis Sets

All subjects that are randomized at Study Visit 1 (baseline visit) are considered study participants. The following study populations and analysis sets will be defined:

Safety Population: This will include all subjects that are randomized to, and receive, one of the trial treatments.

Full Analysis Set: Using the Intent-to-treat (ITT) principle, this will include all subjects that are randomized and receive trial treatment, and attend at least one follow-up post baseline. Subjects will be analyzed according to treatment randomization.

Per Protocol Population (PP): This will include all subjects that are randomized to trial treatment, meet the inclusion/exclusion criteria, do not discontinue treatment within the first nine (9) weeks (- 1 day) and have no significant protocol deviations. Subjects that achieve closure will be included regardless of time on therapy unless they are deemed to have significant protocol deviations or failed to meet the inclusion/exclusion criteria.

Statistical analysis will be performed using each of the subject populations as follows. Analysis of the primary, secondary and exploratory efficacy objectives will be performed separately using both the Full Analysis Set and the Per Protocol Population. All safety analyses will utilize the Safety Population.

The numbers of subjects in each analysis data set will be summarized and listings of patients excluded from each analysis set along with the reasons for exclusion will be provided.

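### The screening-period adverse event summary covers only randomized and treated subjects, so reported run-in events in subjects who entered the run-in but were never treated enter no planned safety summary.

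*SAP*

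**What the plan says.** SAP 4.13 divides AE reporting by period: "Adverse event summaries will separately be presented for the screening period, treatment period" and overall. The section opens with the analysis set for all of it: "All safety analyses and summaries will be conducted using the Safety Population". Protocol 10.4 agrees, with safety work "conducted using the Safety Population. Unless otherwise stated, all safety summaries will be presented by treatment and wound type (DFU or VLU) and overall".

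SAP 4.4 defines the Safety Population: "This will include all subjects that are randomized to, and receive, one of the trial treatments". The derived flag in SAP 4.3, item 2, applies the same rule: "If the patient has received NPWT, then the patient is included in the safety population", and anyone else is left out. Neither document defines a screened, enrolled or run-in analysis set.

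The protocol collects AEs before randomization. Section 9.1.1 (step 12) and section 9.1.2 (step 2) both require reporting of target-ulcer AEs that result from screening or run-in procedures. Section 12.4 sends SAEs of any kind to the AE eCRF, and Table 17-1 marks AE assessment at Run-in Visit 1.

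**The concern.** The run-in is an intervention period. At Run-in Visit 1 the instruction is "Perform ulcer debridement if indicated" (section 9.1.1, step 7), and an iodine dressing is applied, with multi-layer compression for venous leg ulcers (step 11). A screening-period AE table should describe what happened to the people who had this done to them. As planned, it describes only those who passed the run-in and then received negative pressure therapy.

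The omission can depend on the event itself. Section 9.1.2 (step 3) removes a subject with signs of target-ulcer infection as a screen failure, and exclusion 18 in section 7.3.1 does the same for a diagnosed infection requiring treatment. A procedure-related infection can thus take the subject out of the table meant to report it. A reader could take a table headed by the screening period as the experience of everyone who entered the run-in, which it would not be.

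**Working it through.** The plan states no figure on this point and no arithmetic applies. The check is to follow a reported run-in event through the written rules.

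**Step 1. Which subjects reach the AE tables?**
- *Completes the run-in, is randomized and treated.* Safety flag is yes. A run-in AE appears in the screening-period table.
- *Enters the run-in and develops a target-ulcer infection that results from the procedures.* The event is reportable (9.1.2, step 2) and the subject is screen-failed (9.1.2, step 3). No negative pressure therapy is given, so the safety flag is no. The event appears in none of the screening-period, treatment-period or overall tables.
- *Enters the run-in, has a reported AE, and fails for another reason.* Same result.
- *Randomized but not treated.* Safety flag is no. This group should be very small, since randomization and device application are planned for the same visit (9.1.3).

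**Step 2. Does other text bring these subjects back?**
- The words *unless otherwise stated* in SAP 4.13 and protocol 10.4 govern the layout by treatment and wound type. They do not qualify the analysis set.
- Protocol 10.3.3 has a catch-all: "all data collected will be summarized and listed by treatment". It sits under exploratory efficacy and works by treatment. It could reach a subject randomized but not treated, but not one who has no arm.
- Protocol 9.1.1, Note 2: "Screen Failure subjects should have their demographic information captured with the reason for screen failure specified". The Screening Log (7.4) also records reasons for exclusion. Neither supplies AE coding, severity or seriousness.
- SAP 4.5 summarizes numbers screened and randomized and the screening duration. It does not cover AEs.

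None of these repairs the gap for a subject who was never randomized.

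**Step 3. How many, and in which direction?**
The documents give no screen-failure rate and no run-in AE rate. Drop-outs before randomization are replaced (9.2.1), so the target of 160 does not limit how many subjects fall outside the table. The direction is also open. Subjects removed for infection would tend to raise the run-in AE rate, while subjects removed because the ulcer shrank by 30% or more (exclusion 16) might lower it.

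**Step 4. What about earlier screening attempts?**
Up to three attempts are allowed (9.1.1, Note 2). SAP 4.1 keeps only the last screening period unless otherwise stated. SAP 4.5 states an exception for screening duration and SAP 4.13 states none. On the other side, SAP 4.13 also plans an overall summary, and the subject-level AE flags in SAP 4.3, item 45, have no period limit. Whether AEs from an earlier failed attempt of a subject randomized later would be counted is ambiguous.

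**The case against.** The strongest reply is that this is a design choice. Protocol 10.1 and SAP 4.4 both treat only randomized subjects as study participants, and a screening-period table in treated subjects has a use: it separates pre-treatment from treatment-period events in the same people. Titles and footnotes may be clear in the table shells that SAP 1.2 mentions, which are not available here. This explains the Safety Population for the comparison of arms. It does not make a run-in table that depends on passing the run-in a sound account of the run-in.

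Several narrower objections stand and limit the point:
- An infection at Run-in Visit 2 is still recorded as a reason for screen failure, and it is a reportable run-in AE only if it resulted from the procedures.
- Widening the table to everyone who consented would add subjects discharged at Run-in Visit 1 (9.1.1, step 13), for whom that section sets no later AE visit. They would dilute the rate.
- Under sections 12.3 and 12.4, non-serious events away from the target ulcer or leg, such as a reaction to blood sampling, generally stay in source documents. No table built from the eCRF would show them.
- The explicit instruction to record all SAEs in section 9.1.4 concerns the treatment period, so capture of run-in SAEs rests on the general wording of 12.4 and on Table 17-1.

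A reader might infer more than the documents support. They do not show that run-in events are lost: the events are recorded and evaluated by the investigator, and SAEs go to the medical monitor and medical reviewer (12.4). They do not show that the table understates the AE rate, because nothing fixes the direction. They do not show that AEs from earlier failed attempts are definitely dropped.

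**Conclusion.** The gap is real and minor. Under the written rules, reported run-in target-ulcer AEs and any recorded SAEs in subjects who entered the run-in but were never randomized and treated enter no planned safety summary. This includes subjects screen-failed for an infection that resulted from the run-in procedures. Only aggregate reporting is affected. The PICO versus tNPWT safety comparison correctly uses treated subjects and does not change. The size and direction of the effect on the screening-period rate are unknown. The conclusion rests on reading the analysis-set sentence in SAP 4.13 as covering the screening-period summary, which is its plain meaning, and on the unseen table shells not overriding it.

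**What to change.** In SAP 4.13, with an aligning sentence in protocol 10.4:
- Base the screening-period AE and SAE summary on all subjects who entered the run-in (qualified at Run-in Visit 1 and had the run-in dressing applied), by wound type and without a treatment split.
- Limit it to the AE types that the protocol collects before randomization, and say so in a footnote.
- Add a listing of any AE or SAE reported in other consented subjects who were not randomized.
- State that reported AEs from all screening attempts are included, so that the last-period rule in SAP 4.1 does not apply to them.
- Keep the Safety Population for the treatment-period tables.

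The cost is a few sentences and one extra table or listing. The events are already collected, and every subject who starts screening is entered in the web-based system (SAP 1.2). The documents do not say whether the database flags run-in entry for screen failures, so that should be checked when the denominator is programmed. The only other downside is a screening-period AE rate that may look less favourable.
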